#### 1. Summary

This is a prospective double-blinded placebo-controlled block randomised study in intensive care patients comparing intravenous glutamine supplementation (0.285 g/kg body weight/24 h) to placebo. Inclusion criteria are patients treated for more than 3 days. Primary endpoint is a reduction in SOFA-score on day 7 of treatments. Secondary endpoints are: ICU-mortality, 6-months mortality, length of ICU stay, organ failure free days as well as reduction in SOFA-score on day 10 of treatment. Nutrition will be standardised so that not less than 80% of the target which is basasl energy expenditure according to Harris & Benedict is given daily. Enteral nutrition is preferred, but a combination of enteral and parenteral nutrition is recommended to achieve the nutritional target. Diagnosis and APACHE II score are registered at submission. After that the study drug, nutrition and SOFA-score will be registered on a daily basis. For statistical power calculations, a possible effect upon mortality as well as a limited effect of a short treatment period are considered. For statistical comparison non-parametric rank order statistics will be used. To detect a 0.75-point difference in the reduction of SOFA-score on day 7 of treatment, a total of 1,000 patients will be needed. Patients from 20-25 centre in the Nordic countries will be included in the study over a period of 18 months.

#### 2. Abbreviations

Ala-gln	L-alanyl-L-glutamine
APACHE II	Acute Physiologic and Chronic Health Evaluation
g	gram(s)
h	hour(s)
ICU	Intensive Care Unit

kcal	kilocalory(-ies)
kg	kilogram(s)
L	liter(s)
ml	millilliter(s)
mmol	millimole(s)
NaCl	Sodium chloride
SOFA	Sepsis-related Organ Failure Assessment

#### 3. Background

Glutamine is the most abundant amino acid in the body constituting 60 % of the total amino acid and amino nitrogen pool. Together with alanine it accounts for approximately 2/3 of amino acids released from muscle. The concentration of glutamine in human skeletal muscle is high, approximately 20 mmol/l of intracellular water. Considerable changes in glutamine flux and concentration occur in response to a variety of insults such as trauma, infection, fasting and acidosis. A reduction of free glutamine concentration in plasma and tissues is seen postoperatively (1), and it remains decreased and uninfluenced during a period of several weeks regardless of supply of amino acids (2). When glutamine containing amino acid solutions are given the decrease in plasma concentration is counteracted, while the decrease (3,4). Ordinary food is not sufficient to prevent this depletion (5). In postoperative patients glutamine is the last amino acid to be restored back to normal in human muscle (5,6). In critically ill patients in the intensive care unit pronounced and prolonged depletion of muscle free glutamine is seen (7,8). This occurs early in the course and the concentration remains low for a long time. The length of restitution time has so far not been characterised.

Glutamine is a major substrate for the intestinal tract in humans. Both colonocytes and enterocytes utilise glutamine to a greater extent than any other fuel, even glucose (9,10). The glutamine consumption by the intestinal tract is increased by approximately 75% following the stress of a standard elective surgery (11). However, in sepsis and endotoxaemia an impairment in the ability of the intestinal tract to utilise glutamine is sometimes seen (12). Furthermore, glutamine appears to be essential for the normal function and replication of the cells of the immune system shown both in vitro and in vivo (13,14). Due to its instability and low solubility in aqueous solution there has been problems to provide sufficient amounts of glutamine. The dipeptide L-alanyl-L-glutamine is soluble in water and remains stable after heat sterilisation (15). Peptidase activity in all body compartments shows rapid hydrolyses and release of the appropriate amino acids after intravenous infusion.

Modern practise includes provision of enteral feeding to the majority of ICU patients, and only implementing parenteral nutrition when enteral feeding failed or is impractical. However, many diseased conditions in which parenteral nutrition is indicated are accompanied by glutamine depletion. Numerous animal studies and emerging human data document a beneficial effect of enteral and parenteral glutamine supplementation during catabolic states such as infection, surgery, burns, chemotherapy and irradiation, intestinal resection and gut mucosal inflammation (16-23). Available studies suggest that beneficial effects associated with glutamine enriched enteral and parenteral diet formulations are probably due to a number a mechanisms. These include improved protein anabolism (24), enhanced number and function of fixed or circulating immune cells (14,17), maintaining of gut mucosal barrier defences (23), and improved tissue antioxidant status (25).

There are potential advantages of parenteral administration of glutamine as compared to enteral administration. These include increased plasma levels of glutamine which may result in better whole body protein anabolism, antioxidant, and immune function effects. In addition the intestine is able to utilise parenterally administered glutamine via the enterocyte basolateral membrane blood supply, which may be of special importance in patients with damaged mucosa and impaired absorptive capacity and/or high need for glutamine. Provision of glutamine by the enteral route also carries the problem of the discrepancy between prescribed and delivered dose. Furthermore, before enteral nutrition is established there is an uncertainty concerning absorption of administered formula. Therefore the parenteral application is preferable in order to be able to provide glutamine independently of the route of nutrient support.

The glutamine containing dipeptide L-ananyl-L-glutamine is available in a 20% infusion concentrate for central venous infusion after addition to a compatible infusion solution. The concentrated dipeptide solution may also be given separately intravenously in a safe manner.

It may be administered by a central or peripheral vein (26). Dipeptiven is endogenously split into amino acids, glutamine and alanine thereby supplying glutamine with infusion solutions parenterally. The released amino acids are distributed as nutrients into their respective body pools, and are metabolised according to the needs of the organisms. A number of studies have demonstrated the hydrolyses of the dipeptide in man following intravenous administration (27,28).

In current literature no cases with adverse reactions have been reported following administration of the dipeptide in clinical investigations. Still, doses up to 60 g L-alanyl-L-glutamine/day have been administered over a period of 5 days (29-31), and doses of 40 g/day have been administrated over periods up to 25 days (32). Moreover, no adverse physiological effects of the intact dipeptide L-alanyl-L-glutamine have been reported. In a large number of studies L-alanyl-L-glutamine has been demonstrated to be suitable for compensating for glutamine deficiency in patients with normal metabolism and which can thus help maintain intestinal mucosal function. No adverse reactions have been reported in the studies.

The dosage recommendations, as a result of extensive experimental and clinical investigations which are reported in the literature, suggest that an increased intestinal and cellular demand for metabolic fuel in postoperative patients can be met by a daily provision of approximately 15 g of glutamine. In intensive care patients this figure is higher, but less well documented. A supply of 25 g of glutamine daily was sufficient to demonstrate a reduction in 6-months mortality (33).

Nutrition of patients in the intensive care unit is a major treatment modality. Over the years recommendations have varied considerable, reflecting mainly insufficient knowledge concerning the pathophysiology of metabolism in severely diseased states. There are numerous reports about the adverse effects of overfeeding as well as there are substantial documentation concerning the hazards of underfeeding (34,35). The state of the art today is to feed enterally on the level of energy expenditure (36). As measurement of energy expenditure is not a clinical routine, recommendations are often given as kg/kcal/body weight or in accord with formulas of Harris & Benedict. Adding calories considering elevated body temperature, sepsis, extensive burns and so on is not used today in general practice without measuring the energy expenditure by indirect calorimetry.

Modern techniques to administer enteral nutrition have developed and consequently enteral nutrition is today a first hand choice. However, among the patients most in need of nutrition, enteral nutrition is sometimes difficult to administer related to a number of reasons. Therefor when enteral nutrition is considered the only option, undernutrition of the patient is very often seen. Therefor it is necessary to have a routine where complementation of enteral nutrition with parenteral administration is ordinated as soon as the enteral nutrition is insufficient.

Concerning the effects of nutritional treatment upon morbidity and mortality there are a number of international multi-center studies presently (34,37). Most of them suffer from problems of not guaranteeing the individual patient a sufficient nutritional intake in terms of calories and nitrogen. The variability on this point is so large that it basically invalidates any conclusions. The most important point when designing future studies is to have a protocol which guarantees every patient provision of nutrients in accord with the hypothesis.

Another problem is how to define morbidity and mortality. The latter is easily defined although the ICU mortality may be influenced by different routines in individual centres. In addition the beneficial effects attributable to nutritional support may be extended also to the convalescence and rehabilitation period and therefore 6-months mortality is considered a more adequate measurer than in unit or in hospital mortality. Concerning morbidity it may be reflected in the SOFA-score, which take failure in several organs into account (38). As there is a close correlation between SOFA-score and mortality, it may be the best integrated measure of morbidity. Morbidity of clinical importance it may also be reflected in the length of ICU-stay. It is obvious that ICU-stay is variable inbetween units as much as it depends upon the pressure on available ICU-beds and the quality of the post-ICU care. Hospitals with step down units may have quite different routines from those hospitals that lack such a facility. Although there will be considerable differences between units, a block-randomisation may at least to some extent take care of these problems. Still definition of morbidity is problematic, and to choose a measure of morbidity as a primary endpoint must always include a number of compromises.

In addition a close record of the nutrition given is also necessary to verify that the intended treatment is actually received by the patients. The record should include the energy given as well as nitrogen content.

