#### 6:5 Randomisation

Subjects will be randomised to treatment only if they satisfy all inclusion criteria. The trial will include 500 subjects in each treatment group. Block randomisation means that the subjects will be assigned randomly to active or placebo treatment with equal size of the two treatment groups at each investigational centre. A computer program using the method of random allocation within fixed blocks will generate a randomisation list. It will provided for a defined number of subjects and a defined number of reserve subjects at each investigational centre. The randomisation list will be securely locked away during the trial by the responsible statistician until clean file has been declared.

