#### **10. Statistics**

The study is designed with one primary endpoint as the primary objective and several secondary endpoints as secondary objective. The statistical power calculation to determine the sample size is performed for the primary endpoint. Parametric and non-parametric statistics will be used depending on whether the parameters are normally distributed or not. As 3 days of treatment is an inclusion criteria all calculation will be made on included as well as randomised patients (intention to treat)

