#### 10:5 Statistical methods

Student's t-test will be used to compare the 2 groups when variables are normally distributed, this is expected to be the case for the change in SOFA score. For length of stay a rank-test will be used where survival is ranked higher than death and death after a long period of time is ranked higher than death after a short period of time. For mortality a Kaplan-Meyer plot and ?-analysis will be used.

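### The length-of-stay rank test in section 10:5 names no centre stratification although randomisation is blocked by centre, so it is valid but gives up some power

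*Protocol*

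**What the plan says.** Section 3 (Background) discusses length of ICU stay as a measure of morbidity. It states: "It is obvious that ICU-stay is variable inbetween units", and attributes this to pressure on beds, the quality of care after the ICU, and whether a hospital has a step-down unit. It also notes that ICU mortality can depend on local routines. Its remedy is hedged: "Although there will be considerable differences between units, a block-randomisation may at least to some extent take care of these problems".

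Section 6:5 makes centre a stratum of the randomisation, using fixed blocks and "equal size of the two treatment groups at each investigational centre".

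Section 10:5 names the test and part of its ordering: "For length of stay a rank-test will be used where survival is ranked higher than death", with later deaths ranked above earlier ones. Centre does not appear in that description. Sections 10:2 and 10:5 give a Kaplan-Meier plot and a chi-squared analysis for mortality, also without centre. Section 10:4, on the multi-centre design, deals only with recruitment.

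Length of stay is a secondary objective (4:2). On power, section 10 says: "The statistical power calculation to determine the sample size is performed for the primary endpoint".

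**The concern.** Blocking within centre and analysing within centre do different jobs. Blocking gives each unit nearly equal numbers on glutamine and placebo, so unit differences cannot be confounded with treatment. It does not take those differences out of the test's variance. An unstratified rank test compares a patient from a unit that discharges quickly with one from a unit that discharges slowly, and counts that gap as noise. Because the arms are balanced within centre, the treatment contrast does not actually carry that noise. The test therefore uses too large a variance, rejects less often than its nominal level under no effect, and has less power than a test that ranks within centre.

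What is at stake is some sensitivity on a secondary endpoint for which the protocol itself expects considerable unit differences.

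**Working it through.** **The plan's own figure.** The only sample-size figure is for the primary endpoint: 0.75 SOFA points, 80% power, about 500 per group (10:3). Neither SD nor alpha is stated. At two-sided 0.05 it implies SD = 0.75 / [√(2/500) × (1.960 + 0.842)] = 4.23. There is no corresponding figure for length of stay, so nothing in the plan can be reproduced for this endpoint.

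**Inputs.** From the protocol: 1,000 patients in 20 centres (10:4), so 1,000/20 = 50 per centre, allocated 1:1 within centre (6:5). Assumed: two-sided 0.05, ICC of log stay from 0 to 0.20, and survivors ranked with shorter stay as better. Section 10:5 does not state the order among survivors.

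**Step 1, formula.** With 1:1 allocation inside each centre, the true variance of the contrast involves only the within-centre part, a fraction (1 − ICC) of the total. The unstratified test divides by the total. On the correct scale its critical value is c = 1.960/√(1 − ICC). If the stratified test has 80% power, then:

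- unstratified power = 1 − Φ(c − 2.802)
- unstratified type I error = 2[1 − Φ(c)]
- extra patients to offset the loss = [(c + 0.842)/2.802]² − 1

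| ICC | c | Type I error | Power | Loss (points) | Extra patients |
|---|---|---|---|---|---|
| 0.02 | 1.980 | 4.8% | 79.4% | 0.6 | 1% |
| 0.05 | 2.011 | 4.4% | 78.5% | 1.5 | 4% |
| 0.10 | 2.066 | 3.9% | 76.9% | 3.1 | 8% |
| 0.20 | 2.191 | 2.8% | 72.9% | 7.1 | 17% |

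This is exact only for a comparison of means, and approximate for ranks.

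**Step 2, simulated rank tests.** 20 centres of 50, normal log stay, 4,000 replicates per setting, unstratified Wilcoxon against van Elteren. The assumed effect is 0.1815 within-centre SDs without deaths, and 0.27 with 20% deaths ranked lowest (later deaths above earlier ones). Entries are unstratified vs stratified power.

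| ICC | No deaths | 20% deaths |
|---|---|---|
| 0 | 79.2% vs 78.2% | 70.7% vs 70.3% |
| 0.02 | 79.9% vs 79.8% | 69.8% vs 69.7% |
| 0.05 | 78.3% vs 79.0% | 68.2% vs 69.3% |
| 0.10 | 76.8% vs 79.2% | 65.8% vs 69.3% |
| 0.20 | 73.1% vs 79.5% | 61.6% vs 70.0% |

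The Monte Carlo standard error of one entry is about √(0.79 × 0.21/4,000) = 0.6 points, so the differences at ICC 0 and 0.02 are within noise. Under no effect at ICC 0.20 the unstratified test rejected in 3.3% (no deaths) and 4.4% (20% deaths) of trials.

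**Step 3, a second set of assumptions.** Within-centre SD of log stay 0.8, stay 18% shorter on glutamine, ICU mortality 18% with centre logit SD 0.4. Between-centre SD of 0.3, 0.4 or 0.5 gives ICC = 0.09/0.73 = 0.12, 0.16/0.80 = 0.20 or 0.25/0.89 = 0.28. Power was 63% vs 67%, 58% vs 66% and 53% vs 66%. Losses of 4 and 8 points at 0.12 and 0.20 agree with step 2. The 13 points at 0.28 lie beyond the assumed range. With no centre differences the figures were 66.6% vs 65.8%.

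**Step 4, ICU mortality.** Same centres, 18% mortality, centre logit SD 0.4 (an ICC of about 0.024), 20,000 replicates, chi-squared against Cochran-Mantel-Haenszel: 37.7% vs 38.8% (odds ratio 0.75), 67.6% vs 68.4% (0.65) and 80.9% vs 81.5% (0.60). Under no effect, 4.6% vs 4.9%. The gain is 0.6 to 1.1 points.

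**The case against.** The strongest objection is that the protocol never says centres are pooled. It names a rank test without specifying which, and a van Elteren test is a rank test. A reader might infer that all 1,000 patients are ranked together. The text does not go that far: pooling is read from the absence of a centre term, and 10:6 and 10:7 give several analysis sets and remove drop-outs from the length-of-stay evaluation. Centre stratification of a secondary analysis could also sit in an analysis plan that is not at hand. This limits the point to the test as written. It does not dispose of it, because 10:5 fixes the test and spells out an ordering, and read literally that is an unstratified test.

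A reader might also infer that section 3 promises that blocking removes unit differences, and that 10:5 contradicts it. That is not supported. Section 3 claims a partial remedy, says nothing about variance or power, and blocking does deliver the balance. Nor does section 3 say that length of stay is the endpoint most affected.

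Finally, a conservative test does not produce a false claim of benefit, and no power was promised for this endpoint. Both statements are correct and set the severity.

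**Conclusion.** The point holds as one of efficiency. Randomisation uses centre, section 3 expects considerable unit differences in stay, and the length-of-stay test as written does not use centre. If it is run that way, it is valid but conservative.

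The size cannot be derived from the protocol, which gives neither an ICC nor a distribution of stay. Over the assumed range the loss is about 1 point at ICC 0.05 (0.7, 1.1 or 1.5 by method), smaller or nil below that, and about 2 to 8 points at ICC 0.10 to 0.20. It would be tempting to call the length-of-stay result biased or unreliable, but neither follows: balance within centre protects against confounding, and the type I error falls below 5%, not above it. The point does not concern the primary SOFA comparison. For ICU mortality the gain is about 1 point or less, too small to require a change.

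Low severity: a free improvement.

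**What to change.** In 10:5, specify that length of ICU stay is compared with a van Elteren rank test stratified by centre: ranks formed within centre, stratum weights 1/(n + 1). Keep the stated ordering of deaths and survivors. Add a rule for combining very small centres, for example within country, fixed before unblinding. Section 10:4 only calls it desirable that each centre contributes at least 25 patients, so smaller strata may occur.

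Optionally, for consistency with the randomisation, compare ICU mortality with a Cochran-Mantel-Haenszel test stratified by centre.

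The cost is a sentence or two in 10:5 and no new data, since centre is already a stratum of the randomisation. If centres prove alike, the three simulated comparisons without centre differences put the power given up at 0.4, 0.8 and 1.0 points. Fixing the choice in advance also prevents a later selection between stratified and unstratified results.

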## 4. Trial objectives

This trial is designed to elucidate the effect upon morbidity and mortality in intensive care patients given an extra supply of intravenous glutamine for not less than 3 days. All patients should be guaranteed a minimum nutritional support and daily provision of glutamine will continue as long as the patient stay in the intensive care unit.

## 4:1 Primary objective

The primary objective is to compare the change in SOFA-score (Appendix 8:2) on day 7 of ICU stay as compared to the day starting nutritional treatment and glutamine supplementation. Only patients who have received glutamine for not less than 3 days will be considered.

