## 6. Selection and withdrawal of subjects

All patients that receive nutrition in the ICU are eligible for inclusion into the study and may be included until discharge form the unit.

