#### 8:1 Primary objective

The difference in SOFA-score will be calculated from the day starting nutritional treatment as well as glutamine supplementation until day 7 of ICU stay. For patients discharged or dead before day 7, the SOFA score on the day of discharge/death will substitute the latter score. In case of restrictions in treatment, SOFA score will be recorded as long as the nutrition of the patient is maintained.

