#### 10:1 Primary objective

The change in SOFA score between day of start of treatment and day 7 of ICU stay will according to historical data be normally distributed, and therefor the groups will be compared using parametric statistics (Student's t-test). As the primary endpoint will be used in the planned interim analysis after inclusion of 500 patients, an adjustment for the level of significance will be performed accordingly.

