#### 10:3 Sample size

The sample size is calculated to enable detection of a 0.75-point difference in change in SOFA-score after 7 days of treatment with 80% statistical power is based upon parametric statistics. In particular a limited effect during a short treatment period was taken into considerations. The choice of change in SOFA score was partly done on account that it can be assumed to be neutral to a non-identical The sample size of approximately 500 patients in each group are needed under these assumptions.

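### The primary endpoint is read on day 7 of ICU stay but summarised and powered for day 7 of treatment, and with no limit on late entry it is undefined for some patients

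*Protocol*

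**What the plan says.** The protocol puts the primary endpoint on two different clocks.

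- **ICU-stay clock.** Section 4:1 compares the "change in SOFA-score (Appendix 8:2) on day 7 of ICU stay as compared to the day starting nutritional treatment and glutamine supplementation". Section 8:1 calculates the difference "from the day starting nutritional treatment as well as glutamine supplementation until day 7 of ICU stay". Section 10:1 tests "The change in SOFA score between day of start of treatment and day 7 of ICU stay". Sections 4:2 and 8:2 use ICU day 10 for the secondary SOFA endpoint, and section 10:7 defines drop-outs by ICU day.
- **Treatment clock.** The Summary states: "Primary endpoint is a reduction in SOFA-score on day 7 of treatments". It also gives the day-10 endpoint and the sample size by day of treatment. Section 10:3 sizes the trial for a "0.75-point difference in change in SOFA-score after 7 days of treatment".

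Baseline is the day treatment starts in every version. On entry, section 6:1 places screening usually in the first two ICU days, before the trial starts. Section 6 says that patients "may be included until discharge form the unit". The criteria in 6:2 and 6:3 set no latest ICU day. Section 10:6 requires three consecutive treatment periods for evaluation but does not tie them to ICU day 7.

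**The concern.** Baseline moves with the start of treatment while the endpoint day is fixed by ICU admission, so the interval between them shrinks with every day that entry is delayed. Three things follow.

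1. The primary outcome mixes patients with different treatment durations, most of them shorter than the 7 days named in the sample-size statement.
2. For patients who start on ICU day 8 or later the outcome does not exist. The protocol nevertheless promises an intention-to-treat analysis of all randomised patients (sections 10 and 10:6).
3. The protocol supports two different primary endpoints, and the choice between them could be made after data are seen. The interim look after 500 patients (10:1 and 13) uses this endpoint, so the ambiguity also reaches the decision whether to continue.

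The clock applies equally to both arms. The problem is therefore one of definition and dilution, not of bias between arms.

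**Working it through.** **Step 1: treatment days up to and including ICU day 7.** For a start on ICU day s, the count is 7 − s + 1, or zero if s is above 7.

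| Start (ICU day) | Treatment days by ICU day 7 | Days elapsed since baseline |
|---|---|---|
| 1 | 7 | 6 |
| 2 | 6 | 5 |
| 3 | 5 | 4 |
| 4 | 4 | 3 |
| 5 | 3 | 2 |
| 6 | 2 | 1 |
| 7 | 1 | 0 (baseline and endpoint coincide; change is zero) |
| 8 or later | 0 | endpoint precedes baseline; change undefined |

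**Step 2: does another rule cover the late starters?**
- The three-period minimum (4:1, 10:6) does not. A patient starting on ICU day 8 can complete three periods and be evaluable.
- The substitution rule in 8:1 covers only discharge or death before day 7.
- Section 10:7 treats missing data as non-existent, so these patients would simply drop out of the primary comparison.

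**Step 3: the stated sample size.** Section 10:3 gives 0.75 points, 80% power and about 500 per group. It gives no SD, significance level or sidedness, so the 500 cannot be reproduced independently. Assuming a two-sided 5% level, the implied SD is

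SD = 0.75 × √(500/2) / (1.960 + 0.842) = 11.86 / 2.802 = 4.23.

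With a one-sided 5% level it would be 4.77. At two-sided 5%, an SD of 4.0 needs 447 per group and an SD of 4.5 needs 566.

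**Step 4: illustrative dilution.** Assume the effect grows in proportion to treatment days and reaches 0.75 at 7 days. With k treatment days:
- effect = 0.75 × k/7
- power = Φ(2.802 × k/7 − 1.960)
- n per group for 80% power = 500 × (7/k)²

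| All start on ICU day | k | Effect | Power at 500 per group | n per group for 80% |
|---|---|---|---|---|
| 1 | 7 | 0.75 | 80% | 500 |
| 2 | 6 | 0.64 | 67% | 681 |
| 3 | 5 | 0.54 | 52% | 980 |
| 4 | 4 | 0.43 | 36% | 1,532 |
| 5 | 3 | 0.32 | 22% | 2,723 |

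Counting elapsed days instead (4 of 6 for a start on ICU day 3), the effect is 0.75 × 4/6 = 0.50 and power is 46%. If 10% of patients had no exposure and the rest started on ICU day 3, the effect is 0.54 × 0.9 = 0.48 and power is 44%.

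**The case against.** The strongest reply concerns size. The SD is back-solved, so the 80% starting point holds by construction. The fall in power comes entirely from an assumed proportional effect, which nothing in the protocol supports. If most of the effect came early, the loss would be much smaller. Screening usually falls in the first two ICU days, so a start on ICU day 2, with 67% power, is as plausible as day 3. The documents give no distribution of start days, so very late entry is permitted but its frequency is unknown. All of this stands, and the power figures should be read as illustrations.

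Section 10:3 also says that a limited effect over a short treatment period was considered, so 0.75 points may already allow for short exposure. That is possible, but the same section still fixes the powered quantity at 7 days of treatment.

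The ICU-stay clock appears in six sections and the treatment clock only in the Summary and 10:3, so the text could be reconciled the other way. It could, but that would need a limit on late entry and a new sample-size calculation.

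Finally, the substitution of discharge or death scores mixes exposures under either clock, and a treatment clock increases substitution. For a patient starting on ICU day 3, treatment day 7 is ICU day 9. Section 10:4 puts stays beyond 5 days at only about 100 patients in a major centre. This cost is real and the protocol gives no figure for it.

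None of these points removes the two clocks or defines an outcome for patients who start after ICU day 7.

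**Conclusion.** The concern holds and must be fixed. The primary endpoint has two incompatible definitions in current text. The one used in the objective, assessment and analysis sections is not the one that was powered. It gives a change of zero by construction for a start on ICU day 7, and no valid value for a later start. These conclusions rest on the wording alone.

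The size of the power loss is conditional on a two-sided 5% level, the implied SD of 4.23, an effect proportional to treatment days, and all patients starting on the same ICU day. Under those assumptions, starts on ICU days 2 to 4 leave 67% to 36% power in place of 80%. The secondary SOFA endpoint at day 10 has the same fault.

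**What to change.** In sections 4:1, 4:2, 8:1, 8:2, 10:1 and 10:7, replace the ICU-stay day with day 7 (or day 10) counted from the first day of study treatment as day 1. This agrees with the Summary and 10:3. Apply the discharge and death substitution rules on the same clock.

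SOFA is already recorded on each study day (section 8), so no new assessment is needed and the cost is a wording amendment. The downside is that more patients will have left the ICU by treatment day 7 and will contribute a substituted score. How many cannot be derived from the protocol.

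If the ICU-stay clock is kept instead, three changes are needed: set a latest ICU day of entry, correct the Summary and 10:3, and recalculate the sample size for the shorter exposure.
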